## COMPENSATION

To compensate for travel and time spent completing survey measures and basic measurements, study participants will be given a cash voucher in the amount of 60 dollars for the Baseline study visit, 45 dollars for the 6 month study visit, and 50 dollars for the 12 month study visit. This proposed payment is reasonable and commensurate with the expected contributions of participants and is meant to provide additional incentives for participants to complete all 3 study visits. This amount of payment and the terms of the payment are included in the informed consent form. This payment is fair and appropriate and does not constitute undue pressure or influence, or coercion of, the prospective research participant to volunteer for or continue participation in the research study.

## POTENTIAL BENEFIT/RISK

### Benefits:

- *Patients:* The patients who participate in the study will have the opportunity to receive weight management information, and potentially set lifestyle behavior change goals to improve their diet and increase physical activity, which may lead to weight loss and improved health outcomes. Even for patients who do not change their lifestyle behaviors, talking about these topics with trained researchers could serve as support or motivation to move them closer to doing so in the future.
- *Providers and other VA employees:* VA employees who participate in the study may gain improved obesity-related knowledge and patient counseling skills, which could enhance their career, job performance, and satisfaction. Specifically, VA employees may have the opportunity to receive (additional) training in 5As weight management counseling and practice brief motivational interviewing. Training in these could help to facilitate

and/or improve discussions around weight management and health behavior change with patients, as well as encourage the use of individualized techniques to improve diet and exercise and setting health behavior change goals with patients.

Risk:

- *Patients:* This research involves minimal risk for physical, psychological, social, and economic harm. The researchers understand that exploration of these topics and a persons' individual struggle with their weight can be emotionally charged for many people, particularly considering the stigma placed on obesity in our society. The researchers have been trained in order to effectively facilitate conversations on this sensitive topic and will seek to minimize any emotional discomfort you may feel during the study. Additionally, any potential behavior changes related to diet or exercise will be assessed and approved by properly trained individuals including select research staff, the Primary Investigator, and health professionals. Patients will be encouraged to slowly increase their physical activity under the supervision of their PCP. While there is always the risk of injury from starting or increasing physical activity, the benefits usually outweigh potential harms. We will monitor patients for adverse events.
- *VA employees:* This research involves minimal risk for physical, psychological, social, and economic harm.

## MEASUREMENTS

Assessment will occur at the following time points:

- A. Baseline study visit:
  - a. In person: baseline survey, basic physical measurements (weight, height, waist circumference, and blood pressure).
  - b. Remote visit: baseline survey, basic physical measurements (weight and waste circumference) via telephone/video, height and blood pressure results through chart review
- B. Follow-up study visits at 6 and 12 months:
  - a. In person visit: Follow-up in-person questionnaire and basic physical measurements (weight, waist circumference, blood pressure).
  - b. Remote visit: Follow-up questionnaire, basic physical measurements (weight and waist circumference) via telephone/video, blood pressure results through chart review
- C. Follow-up telephone calls (only patients in PAL intervention): Follow-up telephone questionnaire
- D. Chart review: This will occur periodically to assess MOVE! attendance, PACT teamlet visits (documentation of weight management-related conversations), and medical co-morbidities. Outcomes will be assessed through chart review up to 2 years after the baseline visit.

Baseline Data: Prior to the intervention, patients will receive a Baseline survey. To evaluate recruitment for the intervention, baseline data including socio-demographic information, perceived health status, health literacy, perceived environmental factors, and depression will be collected. Co-morbidities will be determined through chart review of the electronic medical record. We will also collect health-related attitudes, beliefs, and baseline behaviors.

Weight & Height: In person visit, study personnel will obtain patient weight measurements using a standardized protocol which includes; 1) weighing without shoes or heavy garments using a digital scale that will be calibrated monthly; at each study time point (Baseline, 6, and 12 months). 2) Height will be measured using the primary care clinic stadiometer and rounded up to the nearest half-centimeter at Baseline. For remote visits, study personnel will obtain Veteran weight measurements via telephone/video using a standardized protocol which includes: 1) weighing without shoes or heavy garments using a digital scale; 2) at each study time point (Baseline, 6, and 12 months). Height will be obtained through chart review.

**Waist Circumference:** Waist circumference will be measured using procedures adapted from National Health and Nutrition Examination Survey (NHANES). In person visit, study personnel will use measuring tape to the nearest quarter inch at the high point of the iliac crest at minimal respiration. This will be measured at baseline, 6, and 12 months. For remote visits, study personnel will guide the Veteran on how to take the waist circumference via telephone/video.

**Blood Pressure:** Study personnel will obtain 2 blood pressure measurements using an automated sphygmomanometer (Omron HEM-907XL). The cuff will be placed on the Veteran's left upper arm, with the bottom of the cuff placed approximately 1|| above the crook of the elbow as per a standard protocol. For remote visits, study personnel will obtain blood pressure through chart review from the Veteran's most recent visit to the VA.

**Feasibility:** We will use process measures from direct observation to determine the feasibility of implementing the PAL intervention at the initial visit. Data on the time to complete the PAL tool, number and types of goals made, number of patients reporting that their PACT teamlets engaged in goal setting conversations, number of reminders completed by the PACT teamlets, time spent doing the intervention, the impact of the intervention on workflow (physician report, qualitative interviews) will be collected. At 6 months into the study period, participating PACT teamlet staff will complete an attitudes survey based on one we have used previously pertaining to intervention implementation. We will also perform qualitative interviews with providers. We will use chart review to note the number of times patients in the telephone support arm actually receive telephone counseling.

**Acceptability:** We will collect data on patient satisfaction with the intervention and the overall visit using patient and provider surveys. We will conduct interviews with participating providers to obtain qualitative data on acceptability.

**Intermediate Outcomes:** Our intermediate outcomes are based on the theory of planned behavior  where motivation and intention to perform a behavior, mediated by self- efficacy, predict behavior change. These constructs will be measured with previously used items that have been adapted for our survey measures by adding other elements of the Theory of Planned Behavior including behavioral beliefs, attitudes, subjective norms, and perceived behavioral control. We will also assess goal attainment at 6 and 12 months.

**Physical Activity (PA) Outcomes:** We will measure duration and intensity using the International Physical Activity Questionnaire (IPAQ) items and accelerometers. The ActiGraph Link (GT9X) accelerometer, worn on the wrist, will be used to objectively measure PA for 7 days at Baseline, and at 6 and 12 months. Study staff will place the Link monitor on the non-dominant wrist to measure PA for 24 hours a day during the Baseline 7-day measurement period. Veterans will then mail the monitor back to the study team in a supplied mailer with postage. At 6 and 12 months, the accelerometer will be distributed to the Veteran with a supplied mailer with postage to be mailed back to the study team. Veterans will not be able to see their data on these monitors so as to minimize measurement influence on PA behaviors. This approach has been used in the NHANES Physical Activity Monitor study. The acceleration data will be used to characterize PA behavior. Examples of PA behavior include steps per day, ambulatory time, as well as daily sum of vector magnitude units per day. The daily sum of vector magnitude units are a quantification of all movement including ambulatory and non-ambulatory activity.

**Behavioral Outcomes:** We will assess diet and physical activity behaviors at Baseline and again at 6 and 12 months. Our main dietary outcomes will be servings of fruits and vegetables, fat intake, refined carbohydrates, and sweetened beverage intake via surveys. A subset of up to 20 participants will complete 24-hour dietary recalls, and this will allow us to assess total energy intake and energy density in this subgroup. Physical activity outcomes will be changes in duration and intensity. We will use chart review to evaluate attendance to TeleMOVE! or MOVE! (# of sessions) pre- and post-baseline visit and 6 and 12 months post- intervention.

Treatment Fidelity: We will do detailed chart reviews using a chart abstraction tool to monitor how often providers see patients and document goal-setting discussions during subsequent visits after the index visit.

#### Data Storage/Security

- *Research Activities:* The following will all take place in private room at the Brooklyn VA with the PI and/or research staff – filling in consent forms, using PAL tool, receiving weight management information, receiving weight management counseling, completing survey measures.
- *Storage of data:* All written data will be kept in locked filing cabinets in a locked room only accessible by the PI and approved study personnel and all electronic data (including survey responses, audio files, and responses to online tool) on secure local VA servers and only accessible on VA password protected computers by the PI and study personnel. Original audio files will be removed from recorders. The data key link will be maintained as a password-protected Excel datasheet on a secure VA Harbor computer within a locked VA Harbor office by the PI, and destroyed upon completion of the final study dataset. The data key link will be kept separate from all survey responses. Only study investigators will perform data entry, access either the surveys or datasets, or perform any analysis of the dataset.
- *Transcription:* For transcription of audio files, files will be sent as encrypted files through the secure server to the VA-contracted transcription company, Transcription Outsourcing, LLC. Transcripts will be de-identified by leaving all identifiable information out of the transcript and using only a unique coded identifier generated by the Principal Investigator. This unique identifier will not use any identifying information (i.e. it will not be generated using the subject's social security number, name, etc.) Recorded information will be transferred to Transcription Outsourcing via a HIPAA-compliant web portal using a VA computer. The transcripts will then be stored and analyzed on a VA secure server. This transcription procedure was approved by the IRB previously (MIRB 01333) under the consultation of the ISO and PO.
- *The PAL tool:* The PAL tool uses a web-interface to ask health questions and collect the data in order to deliver tailored advice. This website will be hosted on either a hired private programmer's server (approved research personnel) or an NYU server. In both cases, Data Use Agreements have been setup with both parties and the VA to protect ownership and use of collected coded data. Data will be regularly migrated from either server (private programmer or NYU) to the VA server via encrypted USB drive. This data storage procedure was approved by the IRB previously (MIRB 01333) under the consultation of the ISO and PO.

Other Quality Control Procedures: The study staff will meet biweekly for the duration of the study to review patient recruitment and data collection procedures to ensure standardization. Research assistants will send reminders to Health Coaches when it is time to call patients in the telephone support arm. To monitor for and address unanticipated adverse events, there will be discussions during meetings with research staff, PI, mentors of PI, and providers/VA staff.

#### **DATA ANALYSIS**

Sample Size and Power Analysis: We base our sample size on within-person weight change at Baseline and 12 months in each arm. We assume an interclass correlation coefficient (ICC) of 0.05 for Veterans within each PCP and an ICC of 0.01 for PCPs within each PACT team. Assuming that at the end of the study we have 5 teams in each intervention arm and recruit and obtain baseline data for 52 Veterans per PACT team (392 Veterans total at 12 months), we will have sufficient power to detect a 2.2kg (SD=6.0kg) difference in weight between the intervention and non-intervention arms. If we do not have PACT attrition (5 PACT teams per arm), then we will have additional power. This amount of weight loss is consistent with findings from the ASPIRE VA study and a systematic review of technology-assisted weight loss interventions in primary care. We will also have the power to detect our hypothesized difference of 15% of PAL Intervention Veterans achieving 5% weight loss (clinically significant—as little as 5% weight loss can improve cardiovascular risk), 85% assuming 12% of intervention arm Veterans achieve this amount of weight loss. We will be able to detect 2.9cm change in waist circumference.

Statistics Analysis: First, all the variables will be summarized using mean with standard deviation and median with interquartile range for continuous variables and frequency table for categorical variables, overall and by randomized arms, respectively. Mann-Whitney tests for continuous variables and Fisher exact tests for categorical variables will be used to check if baseline characteristics are balanced between two arms. Second, Mann-Whitney tests for continuous outcomes and Fisher exact tests for categorical outcomes will be used to compare outcome variables (including intermediate outcomes, behavioral outcomes, and weight outcomes) between two arms at 6 months and 12 months, respectively. Wilcoxon rank tests for continuous outcomes and McNemar tests for binary outcomes will be used to compare them between follow-ups and baseline within each arm. Third, repeated measures modeling based on mixed models will be conducted to compare outcome variables between two arms, utilizing all the data at baseline and three follow-ups. Such modeling can adjust for baseline characteristics, take into account the correlation among repeated measures within subjects, and deal with missing data automatically assuming missing at random. Finally, we will conduct sensitivity analysis based on multiple imputation procedures to examine the impacts of missing data under some missing not at random assumptions.

We will conduct several statistical analyses to describe Veterans participating in the study. Descriptive statistics, including numerical summaries, frequency tables and graphical displays, will be used to present baseline participant characteristics. Exploratory tests, such as chi-square tests and t-tests, will be used to investigate if baseline characteristics are balanced between two randomized arms. Analysis of missing data due to dropout or incomplete surveys will be investigated by inferring a relationship between baseline characteristics/risk factors and 0-1 indicator that defines whether or not a measurement is observed. This analysis will help to identify factors that are likely to be associated with dropout. Additionally, we will investigate whether the dropout rates are different between two arms. For instance, participants with higher levels of motivation may be more likely to be retained in the study. To deal with these missing, we will incorporate the multiple imputation procedure with the regression analyses to be discussed in the following, along with some sensitivity analysis.

In order to assess the impact of neighborhood-level covariates that may help predict weight loss and behavior change, as well as to better understand and report the environmental context of our study participants, we will determine the Veteran's census tracts and block groups. To do this, we will send a csv file containing the patients' addresses to the VA's geocoding service, Geospatial Service Support Center (GSSC), which uses VA's secured proprietary Enterprise Geographic Information System (GIS) software (<https://www.va.gov/oei/docs/va-spatial-data-strategy.pdf>), via the VA's encrypted email. The data will not include the patient's name or apartment number. GSSC will process the data and return a copy of the spreadsheet with the census tract and block group codes added. Once the data is geocoded, the addresses will be purged from the GSSC's database. All applications of geospatial data will be compliant with the objectives and standards established under the VA Spatial Data Strategy (2022).

Qualitative Data: The audio recordings of provider interviews and patients visits will be transcribed by a VA-contracted transcription company (methods used in our previous IRB-approved study MIRB 01333 and MIRB 01496). We will use detailed grounded theory-based procedures including open, axial, and selective coding. After multiple readings of the transcripts and making marginal notes with a second researcher, we will develop, test, and refine a systematic coding scheme of themes and sub-themes, and relationships thereof using NVIVO qualitative data analysis software accessed through VINCI to assist in data analysis and interpretation. Analysis will be facilitated through constant comparison techniques.

## EXPLORATORY AIM

Exploratory Aim: To compare the intervention arm to a third study arm of non-enrolled PC patients matched for age, gender, and BMI ("Usual Care").

Analyzing the Third Arm: We will compare the two randomized study arms (Enhanced Usual Care and PAL intervention) arms with the third study arm of non-enrolled PC patients who are from the same cohort (seen by the same providers and eligible according to the same inclusion and exclusion criteria). Because the third study arm is not randomized, we do not expect the three arms are balanced at baseline characteristics and comparable. We will first identify important

confounders (such as age, gender, BMI) and then use propensity score to adjust for these confounders when comparing the outcomes between the three arms.

## STATISTICAL AND DATA ANALYSIS

First, all the variables will be summarized (intention-to-treat approach) using mean (with standard deviation) and median (with interquartile range for continuous variables and frequency table for categorical variables) overall and by interventions arms, respectively. Then, Mann-Whitney tests for continuous variables and Fisher's exact tests for categorical variables will be used to check if both providers' and Veterans' baseline characteristics are balanced between the intervention arms.

Specific Aims Analysis (main outcomes will be analyzed using intention-to-treat methodology).

### 1. Test the impact of the PAL intervention on weight change, clinical, and behavioral outcomes

1a: Veterans in the PAL Intervention arm will lose 2.2 kg and 27% will achieve  $\geq 5\%$  weight loss after 12 months of treatment. There will be 0kg weight change in the Enhanced Usual Care arm, and 12% will achieve  $\geq 5\%$  weight loss.

1b: The PAL Intervention will result in improvements in behavioral outcomes (e.g., increased number of steps, increased fruit/vegetable intake, increased attendance to MOVE!) and clinical outcomes (blood pressure, Low Density Lipoprotein (LDL), Hemoglobin A1C, and waist circumference).

1c: The PAL Intervention will increase attendance to MOVE! and/or other intensive programs.

Method: The primary outcome is mean weight loss at 12 months. Mann-Whitney tests for continuous outcomes (e.g., weight loss) and Fisher's exact tests for categorical outcomes (e.g., whether or not Veterans achieve  $\geq 5\%$  weight loss) will be used to compare the two intervention arms at 12 months, respectively. Unadjusted confidence intervals will be computed to measure the effects of the PAL intervention on the outcomes compared with the Enhanced Usual Care. Repeated measures modeling based on mixed models will be conducted to compare outcome variables between intervention arms, utilizing all of the data at Baseline and at follow-up visits. Such modeling can adjust for baseline characteristics (e.g., diabetes, gender), taking into account: a) the correlation among Veterans within providers, b) the correlation among repeated measures within Veterans. Model-based adjusted confidence intervals will be provided to measure the effects of the intervention on the outcomes as well. Although repeated measures modeling can address missing data automatically, assuming it is missing at random, we will use a multiple imputation procedure to conduct sensitivity analyses under the practical assumption of missing not at random. The sensitivity analyses will be conducted using pattern-mixture models to examine if the statistical findings are robust when considering several scenarios, including the least-favorable scenario where the missing data from the PAL intervention arm were to follow the same pattern as that of the observed data from the Enhanced Usual Care arm.

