#### Project Methods

To achieve these objectives, we will conduct a cluster randomized controlled trial of 17 PACTs (randomized at the provider level) and 520 of their overweight or obese Veteran patients at the Brooklyn campus of the NY Harbor Healthcare System to study the impact of the 12-month PAL intervention when compared to Enhanced Usual Care. Patients in the PAL intervention will complete the GEM tool and receive health coaching, followed by telephone coaching from the health coach over 12 months. The GEM

tool is a mobile-friendly software program designed to be delivered on tablet computers in the clinic setting to assess lifestyle behaviors and barriers, provide tailored advice and patient education materials, create initial weight loss and behavior change goals, and facilitate counseling by the health coach and PACT staff. Patients in the Enhanced Usual Care arm will receive patient education materials (standard VA Healthy Living Messages) and information on the MOVE! program. All patient participants will attend follow-up visits at 6- and 12-months to assess Body Mass Index, waist circumference, blood pressure, diet, blood tests, physical activity, and goal attainment. PACT staff and health coach outcomes will include 5As-related competency, as well as quality and frequency of counseling. If circumstances restrict the availability of in-person visits (e.g. COVID-19) or based on Veteran's preference, this study will provide a remote/tele-visit option for the baseline and follow up visits.

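### The primary outcome has two planned between-arm analyses, one of which ignores provider clustering, and the plan does not say which decides

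*Combined protocol and SAP*

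**What the plan says.** Project Methods describes a "cluster randomized controlled trial of 17 PACTs (randomized at the provider level", and Study Arms/Randomization also puts the allocation at provider level. Both Sample Size and Power Analysis sections assume an ICC of 0.05 for Veterans within PCP. The second adds a paragraph with 0.03 to 0.04 for Veterans within team.

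Under Statistical and Data Analysis, the Aim 1 Method states: "The primary outcome is mean weight loss at 12 months". It then lists two comparisons of the arms.

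- The first is "Mann-Whitney tests for continuous outcomes (e.g., weight loss) and Fisher's exact tests for categorical outcomes", with this accompanying estimate: "Unadjusted confidence intervals will be computed to measure the effects of the PAL intervention on the outcomes compared with the Enhanced Usual Care".
- The second is a repeated-measures mixed model, "taking into account: a) the correlation among Veterans within providers" and the correlation of repeated measures within Veteran. Its intervals are an addition to the first set: "Model-based adjusted confidence intervals will be provided to measure the effects of the intervention on the outcomes as well".

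The Statistics Analysis paragraph under Data Analysis has the same pair. Its second step is "Mann-Whitney tests for continuous outcomes and Fisher exact tests for categorical outcomes will be used to compare outcome variables" at 6 and 12 months. Its third step is a mixed model, described as follows: "Such modeling can adjust for baseline characteristics, take into account the correlation among repeated measures within subjects". No provider term is mentioned there.

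No section names a primary analysis, an alpha or a sidedness.

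**The concern.** Veterans of the same provider share an arm and, by the plan's own assumption, have correlated outcomes. A Veteran-level Mann-Whitney or Fisher test counts them as independent, so its standard error is too small. The Aim 1 text attaches that test directly to the primary outcome, places it first, and offers its intervals as a measure of the PAL effect on equal terms with the model's.

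Two inferential results would therefore be reported for one primary outcome, one of them anti-conservative, with no rule for which decides. A trial with no true effect could be called positive on the test that ignores clustering while the provider-adjusted model is not significant. A model built from the Data Analysis section alone could also omit the provider term.

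A smaller point is that Mann-Whitney does not estimate the difference in means that hypothesis 1a and the power calculation target.

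**Working it through.** **Inputs.** From the documents: 17 providers; 392 completers, so 392/17 = 23.06, taken as 23 each; SD 6.0 kg; ICC 0.05 (PCP) or 0.03 to 0.04 (team); and, in the second power paragraph, 5 teams per arm with 44 evaluable Veterans each. Assumed: two-sided 5%, equal cluster sizes, normal outcomes.

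**Step 1. The plan's own power.** With 220 per arm, effective n = 220/DE and DE = 1 + (m − 1) × ICC. Taking m = 22 (two PCPs per team, an assumption that the documents do not state):

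- ICC 0.03: DE = 1 + 21 × 0.03 = 1.63, effective n = 135.0, power 85.4% (stated 85%).
- ICC 0.04: DE = 1 + 21 × 0.04 = 1.84, effective n = 119.6, power 80.9% (stated 81%).

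The stated waist and 5%-loss powers also reproduce. With m = 44, weight power would be 71.9% and 64.5%. The sample size therefore already allows for clustering, which the Mann-Whitney and Fisher tests do not.

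**Step 2. Size by formula.** Size = 2 × (1 − Φ(1.96/√DE)). For 17 × 23 at ICC 0.05, DE = 1 + 22 × 0.05 = 2.10 and 1.96/√2.10 = 1.35, so size = 17.6%. On ranks the ICC is (6/π) × asin(0.05/2) = 0.0478, which gives 17.1%.

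**Step 3. Size by simulation.** Null trials were generated as a cluster random effect plus a residual, 20,000 replicates for the main runs. Arms had 9 + 8, 5 + 5 or 10 + 10 clusters. A range in a cell shows repeat runs.

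| Clusters × Veterans | ICC | DE | Formula size | Mann-Whitney size | Unadjusted 95% CI coverage | Mann-Whitney significant, cluster t-test not |
|---|---|---|---|---|---|---|
| 17 × 23 | 0.05 | 2.10 | 17.6% | 17.0–17.3% | 82.2–82.4% | 12.3–12.6% |
| 17 × 23 | 0.04 | 1.88 | 15.3% | 14.8–15.1% | | |
| 17 × 23 | 0.03 | 1.66 | 12.8% | 12.3–13.0% | | |
| 10 × 44 | 0.03 | 2.29 | 19.5% | 19.0% | 80.0% | 14.2% |
| 10 × 44 | 0.04 | 2.72 | 23.5% | 22.4–23.0% | 76.3% | 18.2% |
| 10 × 39 | 0.05 | 2.91 (m = 39.2) | 25.1% | 24.4% | | |
| 20 × 22 (assumed layout) | 0.03 | 1.63 | 12.5% | 11.9% | | |
| 20 × 22 (assumed layout) | 0.04 | 1.84 | 14.8% | 14.1% | | |
| 20 × 22 (assumed layout) | 0.05 | 2.05 | 17.1% | 16.6% | | |

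A t-test on cluster means holds 5.0% to 5.1%. Fisher's exact test at a 12% response rate (17 × 23, ICC 0.05) has a size of about 16%.

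**Step 4. Interval width.** For 17 × 23 the arms hold 9 × 23 = 207 and 8 × 23 = 184, and √(1/207 + 1/184) = 0.1013.

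- Unadjusted half-width: 1.966 × 6 × 0.1013 = 1.20 kg.
- With the design effect: 1.96 × 6 × 0.1013 × √2.10 = 1.73 kg.
- With t on 15 df (2.131) in place of 1.96: 1.88 kg.

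The unadjusted interval is 1.20/1.73 = 69% of the width that clustering requires, against a target effect of 2.2 kg.

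**The case against.** The strongest reply is that clustering has not been overlooked. The Aim 1 Method specifies a provider-adjusted model, the missing-data plan is built around repeated-measures modelling, and the power text uses ICCs. On that reading this is a conventional unadjusted-then-adjusted report, and one label is missing. That is right about the model, and the 17% is the size of one listed test, not the trial's overall false-positive rate. But no section says the model decides, and the simple tests are assigned to compare the arms and measure the effect, not to describe.

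The term unadjusted could mean only without covariates. That does not rescue the tests: provider correlation is attributed to the model alone, and standard Mann-Whitney and Fisher tests assume independent Veterans.

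Three numerical reservations stand.

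- The figures above 17% treat the whole team as the cluster. The power wording permits this, but the stated powers reproduce only with about 22 per cluster.
- The disagreement rate uses a cluster-level t-test in place of the planned model. A random-intercept model with a normal reference gave 11.0% at ICC 0.05 and 6.4% at ICC 0.03.
- Under a pure location shift, Mann-Whitney tests the same null as a comparison of means, so the estimand point is secondary.

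None of these brings the size near 5%.

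**Conclusion.** The concern holds and should be fixed before results are seen. Followed as written, the plan reports a p-value that is too small and an interval that is too narrow for the primary outcome, alongside a model that handles the clustering, and does not say which governs.

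The headline size of about 17%, with coverage of about 82%, rests on the documents' ICC of 0.05, 17 equal providers of 23 completers, and an assumed two-sided 5% level. With 17 providers and ICCs of 0.03 to 0.05 the range is about 12% to 17%. Over all the layouts examined it is about 12% to 24%, at least twice nominal throughout.

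**What to change.** - Name the Aim 1 mixed model as the single primary analysis of the 12-month arm difference in mean weight change. Specify a provider random effect, within-Veteran correlation, and a degrees-of-freedom method suited to few clusters, such as Kenward-Roger or Satterthwaite.
- State alpha and sidedness.
- Replace the Veteran-level Mann-Whitney and Fisher tests and the unadjusted intervals with cluster-valid versions, or label them descriptive with no inferential role.
- Add the provider term to the model in the Statistics Analysis paragraph so that the two sections agree.

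This changes SAP wording only. It needs no new data, and the main model is already planned. The cost is wider intervals and larger p-values than the simple tests would show: in the 17-provider case, a half-width of about 1.73 to 1.88 kg against 1.20 kg.
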